2. OBJECTIVES

2.1 Study Design

The FABREC study is a pragmatic randomized trial of hypofractionation versus conventional radiation therapy in women who have undergone mastectomy and immediate breast reconstruction.

The trial will be conducted at academic and community practice sites to ensure a diverse and representative patient population. Study participants will be randomized 1:1 to conventional fractionation or hypofractionation after mastectomy and breast reconstruction with a tissue expander or implant.

All participants will be assessed for cosmetic and reconstruction outcomes, lymphedema and cancer status through month 18. During the 10-year follow-up period, participants will be assessed for oncologic outcomes (local recurrence, distant disease, and survival) and side effects. Surveys will be used to ask participants to report pain, appearance, mobility, and self-image.

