2.2 Objectives

Objective 1: Compare the effect of short-course versus long-course post-mastectomy radiation therapy on highly-relevant patient-reported outcomes (PROs) and outcomes prioritized by individual trial participants.

Our primary outcome is the Physical Well Being (PWB) domain of the FACT-B instrument. PRO assessment will be further patient-focused, as we will also ask each subject to choose the FACT-B subdomain most relevant to their experience and separately correlate this domain to that patient's radiation schedule. We will thereby create a more

patient-centered outcome by comparing short- versus long-course radiation according to the subscale selected to be most important to the individual patient. In addition, we will assess pain, arm mobility, lymphedema, self-image, satisfaction with decision to undergo reconstruction, sexual well-being, functional well-being, and treatment burden in all patients using standard instruments.

Hypothesis: Short-course radiation therapy will improve patient quality of life in multiple domains.

Objective 2: Compare clinical outcomes for patients receiving short-course versus long-course radiation.

These include complications and clinically-assessed cosmetic results. We will also create an infrastructure to monitor long term oncologic outcomes such as recurrence and breast-cancer specific survival, and rare radiation side effects (secondary malignancy and brachial plexopathy).

Hypothesis: Short-course radiation therapy will decrease complications, improve clinician-quantified cosmetic results, and will have no increased risk of local or regional recurrence or side-effects.

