7. ADVERSE EVENTS REPORTING REQUIREMENTS

Adverse event (AE) monitoring and reporting is a routine part of every clinical trial.

Summary of how to collect and report adverse events (AEs) for the FABREC trial:

1. **Standard Care** All patients will be seen per their treatment plan by an attending radiation oncologist while undergoing treatment. **All adverse events** should be recorded in the patient's medical record per standard practice at your site and managed using clinical discretion. On the Medical Record Review CRFs for the FABREC Study, Clinical Research Professionals (CRPs) will be asked to report AEs as documented in the patients' charts; these medical record reviews will be done at pre-specified timepoints.
2. **Routine Solicited Adverse Events** will not be collected for the FABREC Trial.
3. **Reportable Serious Adverse Events** should be reported using the FABREC Serious Adverse Event CRF each time a reportable SAE occurs. These CRFs should be submitted using InForm. For a list of reportable SAEs, see below.

7.1 **Routine Adverse Events**

Routine Adverse Events will not be collected for the FABREC Trial. **Only events outlined in Section 7.2 should be reported via InForm.**

7.2 **Reportable Serious Adverse Events**

Reportable Serious Adverse Events that occur at any time between initiation of PMRT and 3-years after the initiation of PMRT must be reported using the FABREC Serious Adverse Event CRF. In general, the CRF should be submitted via InForm within 5 calendar days of the AE date. When an adverse event occurs at an institution outside the enrolling site, there may be a delay between when an adverse event occurs and when the study team is alerted to the event. In these instances, it is acceptable for the study team to submit those adverse events in InForm within 5 calendar days of being notified about the event and will not incur a violation.

Only "reportable SAEs" require reporting. For the FABREC trial, a reportable SAE is defined as:

- Grade 1, 2, or 3 **brachial plexopathy** (per NCI CTCAE v 4.03, this AE does not have grade 4 or 5)
- Grade 3 **chest wall pain** (per NCI CTCAE v 4.03, this AE does not have grade 4 or 5)
- Grade 3 **lymphedema** (per NCI CTCAE v 4.03, this AE does not have grade 4 or 5)
- Grade 3, 4, or 5 **myocardial infarction**
- Grade 1, 2, 3, 4, or 5 **pneumonitis**

- Grade 3, 4, or 5 **treatment related secondary malignancy**
- Grade 3, 4, or 5 **wound infection**

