- Unexpected grade 3 or 4 with a possible, probable or definite attribution to PMRT
- Grade 5 (death); all deaths on study require expedited reporting regardless of attribution or causality.
- Local/regional recurrence (not in NCI CTCAE v4)
 - **Note:** We are only interested in following participants who experience local/regional recurrences. When participants experience distant recurrences, they should be withdrawn from the study and all follow-up should be discontinued as these patients may not be monitored for local/regional recurrences due to distant disease.

NCI CTCAE v4 can be downloaded from

http://ctep.cancer.gov/protocolDevelopment/electronic_applications/ctc.htm

Only the events listed above need to be reported in InForm. Events that fall outside the list above do not need to be reported in InForm.

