- **CLINICIAN WITHDRAWAL:** Clinician took participant off protocol treatment (PMRT). Please note that after taking a subject off protocol treatment, study questionnaires and follow-up CONTINUE through the 10-year follow up period. Site study staff should complete all Medical Record Abstraction CRFs and Follow-up CRFs.
- **DEATH:** If a study participant dies, the site staff should complete all Medical Record Abstraction CRFs through death. After all data has been collected through death, sites may take participant off study by submitting the Off-Study CRF via InForm.
- **FOUND TO BE INELIGIBLE:** Participant was enrolled on the trial but was later found to be ineligible. Select one:
 - a. Yes, protocol treatment (PMRT) will continue [treating physician and study chairs agree there are no safety concerns if the patient continues protocol treatment].
 - b. No, protocol treatment will not continue [in this case, study questionnaires and follow up should continue through the 10 year follow up period. Site study staff should complete all Medical Record Abstraction CRFs no matter how long the subject actually received protocol treatment].
- **SWITCHED ARMS:** If inhomogeneity constraints are not attainable in the hypofractionated setting, the patient will be treated with standard fractionation as per protocol. Switching arms in this case is permitted, and these participants who switch arms will still be asked to complete all patient questionnaires and will be followed for 10 years
- **OTHER:** Please specify.
 - **Note:** If a participant experiences a distant recurrence, they should be withdrawn from the study by selecting this option in InForm. Once participants are withdrawn from the study due to distant recurrence, all follow-up should be discontinued.

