Annual Follow-Up Form/Event Monitoring. Participants will be followed for 10-years for long-term outcomes including recurrence, new malignancy, and survival. “Annual follow up 1 of 10” is defined as 1-year after the date on which the participant initiated PMRT. “Annual follow up 2 of 10” is defined as 2-years after the date on which the participant initiated PMRT, and so on through “Annual follow up 10 of 10”. For each annual follow up, if the site has lost track of the participant, then the CSC may send participants the Annual Follow-up Questions sheet (see **Appendix D**) about recent infections, surgeries, and cancer-related issues. Once the CSC receives the completed question sheet, s/he may call participants to follow up on recurrence

and new malignancies. A script for these calls can also be found in **Appendix D**.

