Local/regional recurrence event rate monitoring will occur at the first meeting of the DF/HCC Data and Safety Monitoring Board (DSMB) and continue until the last patient has completed radiation. Data analysis will be performed every 6 months (see Section 11). Specifically, the event rate and corresponding 0.95 exact binomial confidence interval will be calculated, where the numerator is the number of the local/regional recurrence events and the denominator is the number of patients who have completed short-course treatment at time of analysis. The results will be reviewed by the DSMB. If the lower boundary of the 0.95 confidence interval is greater than 2%, accrual of the study will be suspended and a decision will be made as to whether accrual can be resumed or if the study should be closed by the study team in consultation with the DSMB, IRB and study advisory board. The boundary for this criterion is shown in “**Figure: Stopping boundary for local/regional recurrence-event monitoring**”. With the sample size of 200 in the short-course radiation arm, the probability that the interim data meet the stopping criteria (see figure) in the course of the trial is 72% if the true local or regional recurrence rate were 5%. It would be 98% if the true recurrence rate is 8% at 18-months.

Figure: Stopping boundary for local/regional recurrence-event monitoring

There has been no suggestion of increased rare radiation side-effects or mortality with hypofractionation (short-course) radiation therapy with long term follow up in the studies using hypofractionation.^{23,24,31} Therefore, we do not expect any increased risk of side-effects in our short-course arm. Nevertheless, to be extra cautious, we will follow these outcomes in our patients. We recognize that our study is too short to detect differences in long-term distant recurrence, cardiac mortality and overall mortality. Therefore, we will create an infrastructure with which monitor these outcomes and apply for additional funding for longer follow up.

10e. Heterogeneity in treatment (HTE) outcomes

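### Stopping all follow-up at distant recurrence leaves later deaths uncollected, although the protocol names 10-year survival and breast-cancer specific survival as outcomes

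*Combined protocol and SAP*

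**What the plan says.** The withdrawal rule appears twice. In Section 7.2, a note under local/regional recurrence reads: "When participants experience distant recurrences, they should be withdrawn from the study and all follow-up should be discontinued". In Section 8, under the category for other changes in study status: "Once participants are withdrawn from the study due to distant recurrence, all follow-up should be discontinued". The Section 7.2 note says that interest lies only in local/regional recurrence, and gives as its reason that patients with distant disease may no longer be monitored for it.

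The stated outcomes are wider:

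- Section 2.1, for the 10-year period: "participants will be assessed for oncologic outcomes (local recurrence, distant disease, and survival) and side effects".
- Section 2.2, Objective 2, plans an infrastructure to "monitor long term oncologic outcomes such as recurrence and breast-cancer specific survival".
- Section 8, annual follow-up: "Participants will be followed for 10-years for long-term outcomes including recurrence, new malignancy, and survival".
- Section 10c concedes that the study is too short to detect differences in long-term distant recurrence, cardiac mortality and overall mortality, and continues: "Therefore, we will create an infrastructure with which monitor these outcomes and apply for additional funding for longer follow up".

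Death is also a reportable event in Section 7.2 ("all deaths on study require expedited reporting regardless of attribution or causality"), within a limited window: "Reportable Serious Adverse Events that occur at any time between initiation of PMRT and 3-years after the initiation of PMRT must be reported".

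**The concern.** Sites cannot carry out both instructions. Distant recurrence is the event one would expect to precede most breast-cancer deaths, and collection stops there. Deaths after it, their causes, and any later new malignancy or late side effect in these patients would not reach the database.

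If overall or breast-cancer specific survival is later estimated with these patients censored at withdrawal, the censoring is informative: the patients removed are those about to have the highest death rate. Survival would be overstated. The reason given for the rule supports stopping local/regional recurrence review. It does not require dropping vital status.

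**Working it through.** **1. Is there another route to the deaths?**

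| Possible route | Does it recover deaths after distant recurrence? |
|---|---|
| Expedited reporting of death (7.2) | Limited to deaths on study and to 3 years from the start of radiation. A withdrawn patient is probably not on study, and years 3 to 10 are outside the window in any case. |
| Annual chart review, or coordinator contact if the site has lost track (8, 9.1) | No. This is the follow-up that the rule ends. |
| Chart abstraction through death (8, death category) | A general instruction. The distant-recurrence note is specific and covers all follow-up. |
| Change in Study Status form (8) | Records the distant recurrence itself, not what follows. |

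First distant recurrence is therefore captured, as are deaths without prior distant recurrence. Deaths after it are not.

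Other exits in Section 8 are handled differently. After a participant withdraws, chart abstraction runs to year 10 unless record access is refused in writing. After a clinician withdraws a patient from treatment, follow-up runs to year 10.

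**2. How large could the loss be?** The documents give no survival figure to reproduce and no relevant rates. N = 400 is from Section 5.3; everything else is assumed: 10-year distant-recurrence risk p of 10-30%, median survival after it of 2-4 years, and 70-100% of breast-cancer deaths following a recorded distant recurrence.

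Illness-death model, constant hazards, no other-cause death:

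- h = -ln(1-p)/10 (distant recurrence)
- m = ln 2/median (death after it)
- d = hazard of breast-cancer death without recorded distant recurrence, solved to give the assumed share by year 10
- k = h + d; S(T) = exp(-kT), alive and free of distant recurrence
- P(T) = (h/k)(1 - S(T)), distant recurrence by T
- R(T) = h[exp(-kT) - exp(-mT)]/(m - k), alive after distant recurrence
- Uncollected deaths = 400 × [P(T) - R(T)]
- True breast-cancer specific survival = S + R; Kaplan-Meier estimate censored at distant recurrence = exp(-10d)

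Middle case (20%, 3 years, 85%):

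- h = 0.02231, m = 0.23105, d = 0.00247.
- At year 10, S = 0.7805, P = 0.1976, R = 0.0737.
- Uncollected: 400 × (0.1976 - 0.0737) = 49.6.
- True survival: 0.7805 + 0.0737 = 85.4%. Estimate: exp(-0.0247) = 97.6%. Overstatement: 12.1 points before rounding.

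| p | Median (years) | Share | Uncollected by year 10 | True | Estimated | Overstatement (points) |
|---|---|---|---|---|---|---|
| 10% | 4 | 70% | 21.1 | 92.5% | 97.6% | 5.2 |
| 20% | 3 | 85% | 49.6 | 85.4% | 97.6% | 12.1 |
| 30% | 2 | 70% | 85.5 | 69.5% | 89.1% | 19.7 |
| 30% | 2 | 100% | 89.3 | 77.7% | 100% | 22.3 |

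In the last row the estimate is 100% by construction. Between 2.7 (first row) and 15.6 (last row) of the uncollected deaths fall within the first 3 years.

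**3. Overall survival.** A variant with a 2-5% 10-year risk of death without distant recurrence and a median of 2-5 years after it gives 18-89 uncollected deaths, or 49-93% of all deaths. At 20%, 3 years and 5%, 49 of 67 deaths are missed; true 10-year survival is about 83% against an estimate of 95%.

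**4. Earlier endpoints.** Under the same hazards, the proportion with distant recurrence by 6 months is 1 - exp(-0.5h), or 0.5% to 1.8% for p of 10-30%. By 18 months it is 1 - exp(-1.5h), or 1.6% to 5.2%. The loss of questionnaires and photographs is therefore small. For quality of life it is partly covered by the imputation, joint modelling and sensitivity analyses in Section 10b.

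**The case against.** The rule looks deliberate. It appears twice, and Section 7.2 says that local/regional recurrence is the only interest. Section 10 specifies no survival estimand, test or power, Objective 2 promises only an infrastructure, and Section 10c concedes that mortality differences are out of reach. On this view no planned analysis is harmed, and the bias needs an analyst to choose a censoring scheme that nobody has proposed. An endpoint of first distant recurrence or death would not need the missing data.

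Much of this stands. The bias is conditional, and the problem may be aims written too broadly, not collection that is too narrow. But then the aims need changing, because Sections 2.1, 2.2 and 8 still promise survival. Section 10c answers its own limitation by planning to monitor these outcomes, which the rule defeats.

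The size is also open to challenge. With 5% distant recurrence, median 4 years and a 100% share, the model gives about 11 deaths and 2.6 points. The 19.7-point case implies about 37 breast-cancer deaths with no recorded distant recurrence. The direction and the loss of deaths do not depend on these choices.

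Two smaller points are fair. Whether a withdrawn patient counts as on study is undefined, so some deaths in the first 3 years might still be reported. And the other withdrawal categories concern consent or treatment, so handling a disease event differently is not in itself inconsistent.

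**Conclusion.** The concern holds, with high confidence, as a contradiction in the current text that needs no calculation: all follow-up ends at distant recurrence, while survival and breast-cancer specific survival remain stated long-term outcomes. It should be fixed, but it does not threaten the trial's main result.

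On the assumed rates, 21 to 89 deaths among 400 patients would go uncollected by year 10, and breast-cancer specific survival would be overstated by about 5 to 22 points if estimated with censoring at withdrawal. These figures are illustrations for a stage 0-III population whose rates the documents do not give.

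No bias in the between-arm difference is shown. Equal rates in both arms give a difference of 0.0 points, but equal inputs must do so; the result does not show that unequal rates would be harmless. The 6-month primary endpoint and the powered analyses are not materially affected.

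**What to change.** Reconcile Sections 7.2 and 8 (Change in Study Status) with Sections 2.1, 2.2, 8 (annual follow-up) and 10c in one of two ways.

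**Option A: keep the survival outcomes.** Suggested text for both places that carry the rule:

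> At distant recurrence, submit the Change in Study Status CRF. Local/regional recurrence review may stop. The scheduled annual chart review continues to year 10 for vital status and cause of death unless the participant withdraws access to the medical record in writing.

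State also whether new malignancy is still abstracted, and what happens for participants already withdrawn under the present rule. Whether their charts may be reopened depends on the consent form, which was not available for this review.

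**Option B: keep the rule.** Remove or narrow the survival outcomes in Sections 2.1, 2.2 and 8, for example to distant recurrence or death as first event, and align Section 10c.

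**Cost.** Either option is a short amendment. Appendix A requires IRB approval and implementation at participating institutions within 90 days of notification. Option A uses the annual chart review already scheduled to year 10, which already collects mortality (Section 8); its price is modest extra abstraction, for which Section 13.4 offers no additional funding. Option B adds no data collection but gives up the stated survival outcomes.

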7.3 Submission of SAEs to IRB(s)

The Study chairs will submit all applicable SAEs from both Dana-Farber/Harvard Cancer Center sites and outside institutions to the Dana-Farber Cancer Institute IRB per the DFCI IRB Adverse Event Reporting Policy.

Other investigative sites will report AEs to their respective IRB according to the local IRB's policies and procedures in reporting adverse events.

7.4 AE Data Collection and Definitions

AE, date of event, grade, attribution, and relation to an underlying disease or condition will be collected for each AE and SAE.

Grade:

- Grade 1 - Mild AE
- Grade 2 - Moderate AE
- Grade 3 - Severe AE
- Grade 4 - Life-threatening or disabling AE
- Grade 5 - Death related to AE

Attribution:

- Definite – The AE *is clearly related* to the study treatment.
- Probable – The AE *is likely related* to the study treatment.
- Possible – The AE *may be related* to the study treatment.
- Unlikely – The AE *is doubtfully related* to the study treatment.
- Unrelated – The AE *is clearly NOT related* to the study treatment.

Study treatment = PMRT

7.5 Expected Adverse Reactions

Radiation is associated with an increased likelihood of:

- Forming scar tissue around the implant, resulting in long-term problems with increased hardness
- Suboptimal positioning (the implant can migrate on the chest wall) with a need to remove or replace the implant
- Increased risk delayed healing and infection (sometimes requiring removal of the implant)
- Reddening or tanning of the skin
- Desquamation in the treatment field
- Mild pain
- Thickening of the skin

Some radiation side effects associated with lymph node radiation include:

- Lymphedema (potentially related to the extent of surgery)

8. SCHEDULE OF ASSESSMENTS

	Prior to Enrollment (Screening)	Baseline (After participant signs informed consent)	During Radiation Therapy (both arms)	30 Days after RT completion	6 mos. +/- 4 weeks after RT initiation	12 mos. +/- 4 weeks after RT initiation	18 mos. +/- 4 weeks after RT initiation	Every year for 10 years after RT initiation
Medical chart review	X	X		X		X		X
SAE Reporting			Reportable SAEs that occur at any time between initiation of PMRT and 3-years after the initiation of PMRT must be submitted via InForm (see AE section).					
Radiation Treatment Information				X				
Photo Evaluation		X			X	X	X	
Participant Questionnaires		X			X	X	X	
Annual Follow-Up								X

Medical Chart Review. Medical Record Review CRFs will collect data on sociodemographic information, social history, cancer diagnoses, co-morbidities, treatment details, radiation treatment, surgical history and follow up, toxicities, medical history and follow up, disease recurrence, significant clinical events, and mortality.

Study Visits. Because this is a pragmatic trial, there are no protocol mandated study visits. All clinic visits are per standard of care.

Solicited AEs and Expedited SAE Reporting. See Adverse Event Reporting section of protocol for full details.

Radiation Treatment Information. Sites will enter specific information related to the radiation treatment received. This information will be collected by reviewing participants' medical charts at the end of treatment.

Photo evaluation. In order to assess reconstruction, de-identified photos of participant reconstruction will be submitted for evaluation by the Study Chairs or delegate. The participant may take and submit the reconstruction photographs herself (see appendix for patient-facing instructions on how to take and submit reconstruction photographs), or any clinician (nurse, doctor, etc.) who has been trained on the FABREC protocol may take reconstruction photographs.

In extremely rare cases where submission of photographs is not possible, the study chairs will work with the site investigator to complete the Cosmetic Outcome CRFs.

Participant Questionnaires. The following contain items from the following instruments:

- **FACT-B version 4 - Quality of Life** - includes modules for assessing physical well-being, emotional well-being, social well-being, functional well-being and a 2-item question characterizing a breast cancer patient's relationship with her physician. Descriptive statistics for FACT-B have been well characterized.^{33,34}
- **BREAST-Q post-operative, reconstruction module** - Satisfaction with Breast Surgery Outcome - tool was developed at Memorial Sloan Kettering Cancer Center and includes questions regarding changes on the appearance and feel of the reconstruction after radiation therapy.^{35,36} Domains covered by the reconstruction module include satisfaction with breast, satisfaction with outcome, psychosocial well-being, sexual well-being, and chest and upper body physical well-being.
- **Lymph-ICF** - Questions regarding lymphedema, selected from the Lymphedema Functioning, Disability and Health Questionnaire.^{42, 43}
- **Measures of treatment burden** - These questions have been adapted from Kent et al. and the Cancer Care Outcomes Research and Surveillance Consortium (CanCORS) caregiver survey.^{44, 45, 46} The measures of treatment burden will only be administered at the 6-month time-point.
- **Sociodemographics and social/medical history.**

Change in Study Status. Whenever there is a change in a participant's status on the study including the development of a distant recurrence or metastatic disease, the Change in Study Status CRF should be completed and submitted via InForm within 5 business days of the change.

Reasons a participant might have a change in study status include:

- **ACTIVE PARTICIPANT WITHDRAWAL:** Study participant actively withdrew consent for one or more components of the study, including:

- a. protocol treatment (PMRT), and/or
- b. participant contact for questionnaires and follow up, and/or
- c. access to his/her medical record for Medical Record Abstraction.

HOW TO PROCEED: Unless the participant explicitly (in writing) withdraws consent to access his/her medical record, site study staff SHOULD complete all Medical Record Abstraction CRFs and all Follow-up CRFs through the end of the 10-year follow up period.

- **CLINICIAN WITHDRAWAL:** Clinician took participant off protocol treatment (PMRT). Please note that after taking a subject off protocol treatment, study questionnaires and follow-up CONTINUE through the 10-year follow up period. Site study staff should complete all Medical Record Abstraction CRFs and Follow-up CRFs.
- **DEATH:** If a study participant dies, the site staff should complete all Medical Record Abstraction CRFs through death. After all data has been collected through death, sites may take participant off study by submitting the Off-Study CRF via InForm.
- **FOUND TO BE INELIGIBLE:** Participant was enrolled on the trial but was later found to be ineligible. Select one:
 - a. Yes, protocol treatment (PMRT) will continue [treating physician and study chairs agree there are no safety concerns if the patient continues protocol treatment].
 - b. No, protocol treatment will not continue [in this case, study questionnaires and follow up should continue through the 10 year follow up period. Site study staff should complete all Medical Record Abstraction CRFs no matter how long the subject actually received protocol treatment].
- **SWITCHED ARMS:** If inhomogeneity constraints are not attainable in the hypofractionated setting, the patient will be treated with standard fractionation as per protocol. Switching arms in this case is permitted, and these participants who switch arms will still be asked to complete all patient questionnaires and will be followed for 10 years
- **OTHER:** Please specify.
 - **Note:** If a participant experiences a distant recurrence, they should be withdrawn from the study by selecting this option in InForm. Once participants are withdrawn from the study due to distant recurrence, all follow-up should be discontinued.

Annual Follow-Up Form/Event Monitoring. Participants will be followed for 10-years for long-term outcomes including recurrence, new malignancy, and survival. “Annual follow up 1 of 10” is defined as 1-year after the date on which the participant initiated PMRT. “Annual follow up 2 of 10” is defined as 2-years after the date on which the participant initiated PMRT, and so on through “Annual follow up 10 of 10”. For each annual follow up, if the site has lost track of the participant, then the CSC may send participants the Annual Follow-up Questions sheet (see **Appendix D**) about recent infections, surgeries, and cancer-related issues. Once the CSC receives the completed question sheet, s/he may call participants to follow up on recurrence

and new malignancies. A script for these calls can also be found in **Appendix D**.

